The interviews will be recorded for subsequent transcription of the interactions. The transcribed interviews will be examined for common themes. Each interview will vary between 20 and 30 minutes and will be performed by a member of the Mindful Breathing Laboratory who is trained in Motivational Interviewing and Qualitative Interviewing. Additional members from the Lab will assist in the transcription of the interviews as well as theme identification. Data collection and analysis will be overseen by [name]. (A guided interview script will be used.)

In addition, the five Mayo Clinic staff who served as health coaches on the study will also be offered the opportunity to be interviewed to learn their experiences in the program. The interviews will be conducted by Qualitative Expert, [name], either in a private space or by phone call. The interview will be recorded so that it can later be transcribed and analyzed. An email inviting the health coach to participate will be sent to the health coach. The health coach will be orally consented and will have the option to opt out.

[figure not shown]

Fig. 9. Randomized study design.

Questionnaires:

Physical QOL will be assessed by the CRQ (Aim 1), SM abilities, self-efficacy (Aim 2), and daily PA and self-efficacy for exercise (Aim 3). These QOL components will be measured at baseline, three, six, and nine months after randomization in both groups. Qualitative analysis (Aim 4) will occur after the intervention in order to further understand the intervention's acceptability and to help interpret the comparative effectiveness findings from Aims 1-3.

Additional QOL questionnaires will include the Interpersonal Support Evaluation List (ISEL-12), the Meaning of Life Questionnaire (MLQ6), and the Longitudinal Analogue Self-Assessment (LASA6). Recent research has indicated that social support and sense of meaning of life are important indicators in the perception of quality of life. The added questionnaires will better measure these important factors.

Study Sites:

The clinical study sites include (1) Mayo Clinic—Rochester, Rochester, MN, (2) Mayo Clinic-Jacksonville, Jacksonville, FL, and (3) HealthPartners® Specialty Center-Regions Hospital, St. Paul, MN. The engineer site is Minnesota HealthSolutions, Maple Grove, MN. These study partners have collaborated for the past five years.

Recruitment

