The study coordinator will utilize ACE to generate a list of eligible participants with research authorization (avoiding any HIPAA noncompliance) and send invitation letters. In addition, patients presenting to the clinic with COPD may be referred to the study by

their provider. The coordinator will approach potential participants through a screening call (review inclusion and exclusion criteria) and will schedule an enrollment visit and to demonstrate the Home Rehab and to obtain consent.

Subject Information

Target accrual:

400 total participants. Mayo Clinic Rochester has a target enrollment of 150 participants, Mayo Clinic Florida and Health Partners have a target enrollment of 70 participants each. Up to fifteen total participants will be enrolled in a Pilot Study.

Inclusion Criteria:

- Clinical diagnosis of COPD, confirmed by spirometry
- Age ≥ 40 years (to avoid recruiting participants with asthma rather than COPD)
- Current or previous smoker (≥ 10 packs per year)
- Confidence in using the proposed PR system
- English language fluency

Exclusion Criteria:

- Study candidate experiencing an acute COPD exacerbation (can be included after the acute event)
- Inability to walk (orthopedic-neurologic problems or confined to a bed)
- Currently in PR or finished PR in the last three months (unlikely to improve)
- Pregnant women
- Live in an area where cell phones do not work/

Research Activity

Randomization

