Eligible participants (after the screening call) will visit the site for the consenting process. In the clinic visit, all consented participants will receive baseline questionnaires, and information about the system. They will complete the questionnaires during the visit, and take home the ActiGraph™ AM (Fig. 10), to wear for one week. On return of the AM, the study coordinator will randomly assign the participant to intervention or attention waitlist control through a centralized program, Research Electronic Data Capture (REDCap). Randomization will be stratified by whether the participant has poor lung function (forced expiratory volume [FEV1] $<50\%$ predicted) and whether the participant has severe dyspnea (recorded modified Medical Research Council Dyspnea Scale [mMRC] score, 3-4; scale, 0-4); critical factors that can make the study arms unbalanced regarding risk factors. The study coordinator will call the participant and inform him or her of the results of randomization. Intervention participants will be mailed the home-based PR system (pulse oximeter, tablet and Garmin Vivofit™). While blinding participants will not be possible, as most behavioral interventions, the arms will be blinded to the research team in charge of the data entry and statistical analysis and revealed only at study conclusion.

Clinic Visit: Face-to-Face Encounter

The participant will practice the use of the proposed system and the PR routine in the PR lab to ensure understanding and safety; therefore, no home visits are planned. The clinic visit is the best opportunity to evaluate the confidence of the individual in using the system. The study team will provide step-by-step instructions on how to perform the daily home-based PR routine (Fig. 11) and discuss the home environment where PR will take place to define the optimal conditions, particularly safety, for exercise. The participant will be asked to rate their confidence to use the technology presented and their confidence (self-efficacy) to perform the home rehabilitation routine on a scale from 0 (no confidence) to 10 (great confidence). A rating of six or greater will be deemed an acceptable confidence level to participate in the study.

Fig. 10.
ActiGraph™
wGT3X-BT.

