The target population consists of patients who have COPD receiving outpatient care at Mayo Clinic (Rochester). We plan to enroll 200 patients in the study through referral from the Mayo Clinic Pulmonary Division ACE Database. Once enrolled, study staff will review the medical records and will document the most recent Pulmonary Function Test data and demographics.

Subjects	Alerts	Messages	Display	Activity Monitor		Exercise and Walking			Check In Questionnaire	
				Subject Id	Synchronized	Ave Step Count	Performed	Pulse Ox	Ave Duration	Concerns
prt0001				prt0001	3 Days Ago	1402	2 Days Ago	●	4.4	2 Days Ago
prt0002				prt0002	4 Days Ago	7900	5 Days Ago	●	8.4	5 Days Ago
prt0003				prt0003	Yesterday	10289	7+ Days Ago		0.0	7+ Days Ago
prt0004				prt0004	7+ Days Ago	0	7+ Days Ago		0.0	7+ Days Ago
prt0005				prt0005	6 Days Ago	0	7+ Days Ago		0.0	7+ Days Ago
prt0006				prt0006						
prt0007				prt0007	Yesterday	9733	Yesterday	●	17.2	Yesterday

Fig. 13. Overview report.

[figure not shown]

Fig. 14. Weekly individual report.

[figure not shown]

Fig. 15. Detailed report.

HIPAA Identifiers and Protected Health Information (PHI)

Check all that apply:	INTERNAL	EXTERNAL
Name	X	
Mayo Clinic medical record or patient registration number, lab accession, specimen or radiologic image number	X	
Subject ID, subject code or any other person-specific unique identifying number, characteristic or code that can link the subject to their medical data	X	
Dates: All elements of dates [month, day, and year] directly related to an individual, their birth date, date of death, date of diagnosis, etc. Note: Recording a year only is not a unique identifier.	X	
Social Security number		
Medical device identifiers and serial numbers		
Biometric identifiers, including finger and voice prints, full face photographic images and any comparable images	X	
Web Universal Resource Locators (URLs), Internet Protocol (IP) address numbers, email address		
Street address, city, county, precinct, zip code, and their equivalent geocodes	X	
Phone or fax numbers	X	
Account, member, certificate or professional license numbers, health beneficiary numbers		
Vehicle identifiers and serial numbers, including license plate numbers		
Check 'None' when none of the identifiers listed above will be recorded, maintained, or shared during the conduct of this study. (exempt category 4)	 None	 None

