Integration with Aims 1-3: The function of the mixed-methods design is elaboration of the quantitative data on effectiveness with the qualitative findings. After initial quantitative and qualitative analyses are complete, the investigators will place findings side-by-side to explore connections as well as divergent findings that need further exploration. This includes within- and between-case analysis to understand the perspectives of participants who differed on comparative effectiveness outcomes (Aim 1-3) as well as those who differed in important baseline characteristics such as participant activation.

Sample Size: We will enroll a total of 200 participants, with 100 in each arm. Sample size calculations are based on two-sample, two-sized t-tests comparing the two groups at 3 months. **Aim 1:** We calculated the sample size based on estimates from our previously published data⁶. From this research, the CRQ has a SD of about 1.13. A total sample of 189 participants (94 or 95 per group) is needed to detect a difference of 0.5 (the minimal clinically important difference) in the CRQ with 80% power. Based on our previous health coaching application (R01HL09468 [name], PI),⁶ we expect 5% attrition. We will therefore enroll 200 participants, 100 in each arm.

Aim 2: A sample size of 128 is needed to detect a half SD change in SMAS-30 based on COPD studies using this measure. **Aim 3:** The number of steps recorded by the AM is considered a valid measure of PA in patients with COPD and the elderly. The clinically meaningful difference in steps is estimated at 1100. Therefore, a sample size of 170 participants (85 per group) is needed considering a SD of 2500 steps from our previous study.⁶ **Aim 4:** The sample size of 40 completed participant interviews is within standards for qualitative research, but interviewing and analysis will take place concurrently and iteratively to inform the sampling plan. We will continue interviewing until saturation (the point at which interviews are not yielding much new information) is reached; the sample

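### The protocol gives three enrolment totals (400, 290 by site, and 200 in the sample-size section) and nothing reconciles them

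*Combined protocol and SAP*

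**What the plan says.** The figures stand in four places in the combined protocol and SAP (Version 9).

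- **Subject Information, Target accrual:** "400 total participants. Mayo Clinic Rochester has a target enrollment of 150 participants". The same sentence continues: "Mayo Clinic Florida and Health Partners have a target enrollment of 70 participants each". Up to fifteen pilot participants are then mentioned; the Pilot Study paragraph says that they are not randomised.
- **Study Sites:** besides Rochester, the clinical sites are "2) Mayo Clinic-Jacksonville, Jacksonville, FL, and (3) HealthPartners® Specialty Center-Regions Hospital, St. Paul, MN". The only other partner listed is an engineering site.
- **Sample Size:** "We will enroll a total of 200 participants, with 100 in each arm". The basis for Aim 1 is "A total sample of 189 participants (94 or 95 per group) is needed to detect a difference of 0.5" with 80% power and an SD of about 1.13. Attrition of 5% is then allowed for, and the 200 is stated a second time.
- **Review of medical records (Category 5):** "We plan to enroll 200 patients in the study through referral from the Mayo Clinic Pulmonary Division ACE Database". That paragraph describes its target population as Rochester outpatients only.

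The Randomization section puts consent, baseline questionnaires and a week of activity monitoring before allocation: "On return of the AM, the study coordinator will randomly assign the participant to intervention or attention waitlist control".

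**The concern.** A total and its site breakdown stand side by side and do not agree, and neither agrees with the sample size that the analysis plan justifies. Stopping at 200, 290 or 400 would each comply with some part of the protocol. A reader of the results could not tell whether the final N was the planned one. If the larger figures count randomised participants, 90 to 200 people would be enrolled beyond the number the plan justifies, with no reason given. The choice also affects how a significant result is read, because a larger trial can detect differences well below the 0.5 points that the plan calls the minimal clinically important difference.

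**Working it through.** **1. Site sum (Target accrual).** 150 + 70 + 70 = 290. With the pilot: 290 + 15 = 305. Shortfall from 400: 400 − 290 = 110, or 400 − 305 = 95. Excess over the Sample Size section: 290 − 200 = 90, and 400 − 200 = 200.

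**2. The records-review figure.** Its 200 most simply repeats the trial total. Read literally as a Rochester figure, it conflicts with Rochester's target of 150, and 200 + 70 + 70 = 340 matches neither 400 nor 200.

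**3. The plan's step from 189 to 200.** 189 / 0.95 = 198.9, so 199, rounded to 200. This reproduces. The 5% attrition is already used here and cannot also link 200 to 290 or 400.

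**4. Loss before randomisation needed to link the totals.**
- 400 to 290: 1 − 290/400 = 27.5%
- 290 to 200: 1 − 200/290 = 31.0%
- 400 to 200: 1 − 200/400 = 50%

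No such rate is stated.

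**5. The plan's 189.** Inputs: difference 0.5 and SD 1.13 (Sample Size); two-sample t-test, two-sided 5% (Analysis Plan); equal allocation (Randomized Study). The normal approximation per arm is

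n = 2 (1.960 + 0.842)² × (1.13/0.5)² = 2 × 7.85 × 5.108 = 80.2, so 81 per arm, 162 in total.

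The noncentral t calculation gives 81.15, so 82 per arm, 164 in total. With 5% attrition, 164 / 0.95 = 172.6, so 174 in equal arms. The 189 does not reproduce: at 94 or 95 per arm, power is 85.7%. An SD of about 1.22 would give 189 at 80% power. With SD 1.13, 85% power needs 186, which is close, but 85% is not the stated power.

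**6. Aim 1 at each candidate total.** Assumption: each figure is the number randomised, with 5% attrition. Evaluable per arm is m = 0.95 N / 2, and the noncentrality is 0.5 / (1.13 √(2/m)).

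| N | m per arm | Noncentrality | Power for 0.5 | Difference detectable with 80% power |
|---|---|---|---|---|
| 200 | 95 | 3.05 | 85.9% | 0.46 |
| 290 | 137.75 | 3.67 | 95.5% | 0.38 |
| 400 | 190 | 4.31 | 99.0% | 0.33 |

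If 290 or 400 are consent or screening numbers, those two rows do not apply.

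**The case against.** The strongest defence is that the analysis plan does have a defined N. The Sample Size section is the only place where a number is derived, it states 200 twice, and its attrition step is consistent. On that view 400 and 290 are administrative accrual figures. They may exceed the randomised number because people can drop out between consent and allocation: the clinic visit requires a confidence rating of at least six to take part, and randomisation waits for the return of the activity monitor. The harm is also modest: no candidate N is underpowered for Aim 1, and the 190 evaluable expected from 200 also cover the 128 and 170 that the plan requires for Aims 2 and 3.

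Part of this stands. The 200 is the only figure with a derivation, and the consequence for power is benign. The complaint about unjustified extra enrolment holds only if the larger figures count randomised participants.

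The rest does not close the gap. Target accrual and Sample Size both speak of enrolment, no loss rate before randomisation is given, and such losses could not explain why a total of 400 and site targets adding to 290 stand in the same entry. Phase 2 in the Randomized Study section changes the contacts that controls receive and is not said to add participants. Phase 3 interviews people who have already completed the intervention.

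**Conclusion.** The concern holds. The current text gives 400, 290 (305 with the pilot) and 200 as enrolment figures, and none follows from another by any stated rule. This leaves the planned randomised N and the end of accrual ambiguous, and the sample-size justification does not match the accrual target. It should be fixed, but it does not threaten power: on the plan's own SD and difference, with 5% attrition, every candidate gives at least about 86% for Aim 1 if it is the number randomised.

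The 189 is a separate, smaller fault. It exceeds the 164 that its inputs require, so it makes the trial larger than the stated 80% power needs. The contradiction over enrolment does not depend on it.

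**What to change.** - State one randomised N, with site targets that add to it.
- If 400 or 290 is a screening or consent number, say so, give it separately, and state the expected loss before randomisation.
- Say that the pilot participants are outside the randomised N.
- Make Target accrual, the records-review paragraph and Sample Size agree, and say whether the records-review figure covers all sites or Rochester only.
- Restate Aim 1 power and the detectable difference for the chosen N, and correct or explain the 189.
- The documents do not say that the target was raised from 200. If it was, record that, give the reason, and confirm that no between-arm outcome data informed the change.

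The cost is protocol wording and one recalculated power statement. Fixing N at 200 adds no participants to the powered design. Fixing it at 290 or 400 adds 90 or 200 and would need its own justification.

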Data will be stored in Mayo Clinic's REDCap database. Mayo Clinic Florida and Health Partners will only be able to see data from their site. Mayo Clinic Rochester will have access to data entered into REDCap as they are the coordinating site for this trial. REDCap (Research Electronic Data Capture) is a secure, web-based application designed to support data capture for research studies, providing: 1) an intuitive interface for validated data entry; 2) audit trails for tracking data manipulation and export procedures; 3) automated export procedures for seamless data downloads to common statistical packages; and 4) procedures for importing data from external sources.

Health Coaches located at Mayo Clinic Rochester may fill in as Health Coaches at other sites to cover vacations, absences and employment gaps in health coaches. Mayo Clinic Rochester Health Coaches only have access to data in REDCap (demographics and health coach notes) and not the medical record.

Data Analysis and Data Safety Monitoring

DSMB

See Data Safety Monitoring Charter.

Analysis Plan

Page 11 of 17

There are three *distinct* quantitative study hypotheses (inform different aspects of the process). Hypothesis 1 (Aim 1) states that participants on home-based PR will have higher physical (dyspnea fatigue) QOL at month three than participants in the waitlist control group as measured by the CRQ physical summary score. Hypothesis 2 (Aim 2) is that participants on home-based PR will have better SM abilities at month three than participants in the waitlist control group. The SMAS-30 will be used to test this hypothesis. Hypothesis 3 (Aim 3) is that participants on home-based PR will have more daily PA than participants in the control group at month three. This will be measured by steps and minutes spent in sedentary, light, and moderate activity measured by the ActiGraph^{34,35} and greater self-efficacy for exercise. This study has two activity monitors, the ActiGraph, a gold standard activity monitor used for outcome measures (7-day wearing) at baseline, 3, 6 and 9 months. The Garmin Vivofit PR activity monitor used daily during PR period will NOT be used as an outcome measure, just for health coaching and participant awareness of physical activity (participant will keep this activity monitor after PR).

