For the continuous study outcomes, changes from baseline to three months will be compared between the study arms using two-sample, two-sided t-tests with 5% type I error rates. Changes in QOL and number of steps will be compared between the two treatment sequences using two-sample two-sided t-tests. No adjustments will be made for multiple testing. Means, SDs, medians, ranges, and frequency distributions will be reported and plotted over time by study arm. Additional analyses will compare changes from baseline to three months. Linear models will be used to assess the impact of treatment arm on three month outcomes after adjusting for the corresponding baseline measure and other variables related to the outcome (age, degree of breathlessness at baseline using the mMRC, and FEV1). Repeated measures mixed models will be used to estimate the intervention effect over the three months of the comparison study. Although there is a crossover element to the study design, crossover analyses will not be used due to the anticipated carryover effect in the intervention arm. Intent-to-treat analyses will also be performed to determine the sensitivity of the results to dropouts and missing values. In the intent-to-treat analyses, if a month three measure is missing for any reason, it will be described as not changing from baseline. Health care utilization (number of ED visits, hospitalizations, and length of stay) between baseline and three months will be treated (analyzed) as both binary (for incidence rates) and continuous (for the number of events). The binary endpoints will all be compared between groups using Fisher's exact test. Logistic regression models will also be fit to look for differences in these outcomes by arm after adjusting for age, mMRC, FEV1, baseline levels of anxiety, depression, and fear, and baseline health care utilization (before starting the study). While significant missing-ness (>5%) in the Aim 1 outcome is not expected, imputation is planned in case it is.

Descriptive summaries of the changes between baseline, three, six, and nine months will be used to assess the effect of the delayed intervention on the control arm and the residual beneficial effect on the intervention arm. These results will be only descriptive and exploratory. No formal hypothesis testing will be done. All data will be stored in REDCap and analyzed using SAS (Cary, NC).

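### Hypothesis 3 (more daily physical activity) has five unranked measures, unadjusted 5% tests and no deciding measure, although Aim 3 was sized on steps alone

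*Combined protocol and SAP*

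**What the plan says.** The Analysis Plan sets out three hypotheses. Hypotheses 1 and 2 each name one instrument: the CRQ physical summary score and the SMAS-30. The third reads: "Hypothesis 3 (Aim 3) is that participants on home-based PR will have more daily PA than participants in the control group at month three". Its measurement is then given as "This will be measured by steps and minutes spent in sedentary, light, and moderate activity measured by the ActiGraph", followed by "and greater self-efficacy for exercise". That makes five measures. The Questionnaires paragraph under Study Design and Methods also assigns self-efficacy for exercise to Aim 3.

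For testing, the Analysis Plan says that for continuous outcomes "changes from baseline to three months will be compared between the study arms using two-sample, two-sided t-tests with 5% type I error rates", and shortly afterwards: "No adjustments will be made for multiple testing".

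The Sample Size section treats Aim 3 through one measure only. "The clinically meaningful difference in steps is estimated at 1100", and "a sample size of 170 participants (85 per group) is needed considering a SD of 2500 steps". The other four Aim 3 measures have no target difference, no SD and no sample size.

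**The concern.** Hypotheses 1 and 2 each stand or fall on one result at month three. Hypothesis 3 yields five results, and the plan gives no deciding measure, no order among them and no rule for how many must be significant. The plan's remark that the three hypotheses are distinct can explain not adjusting between aims. It does not address several measures inside one aim.

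At stake is how an Aim 3 claim can be read. An isolated result on light minutes, say, could be reported as success for Aim 3 while steps, the measure the aim was sized on, show nothing. Self-efficacy for exercise is not physical activity, so a result on it alone could be offered for Aim 3 with no change in activity at all. In either case the 5% attached to each test would not be the error rate of the claim.

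**Working it through.** **Inputs from the documents.** Five measures for Hypothesis 3; two-sided 5% per test; no adjustment (Analysis Plan). Steps: difference 1100, SD 2500, 170 participants or 85 per group. Enrolment: 200, 100 per arm, with 5% attrition expected, which leaves 95 per arm (Sample Size).

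**Assumptions.** Power of 80% for Aim 3, which the documents state only for Aim 1. Correlations between the five test statistics, which the documents do not give.

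**Step 1: the plan's own figure.** By the normal approximation, n per group = 2 × (1.960 + 0.842)² × (2500/1100)² = 2 × 7.849 × 5.165 = 81.1, so 82 per group and 164 in total. The t-test calculation, which matches the planned test, gives 83 per group and 166 in total. The stated 170 is within 3% of that and gives 81.4% power. The Aim 3 sample size is therefore a calculation for one test of steps at an unadjusted two-sided 5%.

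**Step 2: independent tests.** If no measure is truly affected and any one significant result counts:
- five measures, two-sided: 1 − 0.95⁵ = 22.6%
- four ActiGraph measures, two-sided: 1 − 0.95⁴ = 18.5%
- five measures, favourable direction only: 1 − 0.975⁵ = 11.9%, against 2.5% for one test

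**Step 3: correlated tests.** Simulation of normal test statistics with a common correlation (2,000,000 draws, critical value 1.96), each measure signed so that positive is favourable:

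| Assumed correlation | Five measures, two-sided | Four ActiGraph measures, two-sided | Five measures, favourable direction |
|---|---|---|---|
| 0 | 22.6% | 18.5% | 11.9% |
| 0.3 | 20.9% | 17.4% | 10.5% |
| 0.5 | 18.3% | 15.6% | 9.2% |
| 0.7 | 14.8% | 13.0% | 7.4% |
| 0.9 | 10.2% | 9.4% | 5.1% |

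A single common correlation is a simplification. Three assumed patterns, with the activity measures correlated 0.2 to 0.9 among themselves and self-efficacy only weakly linked to them, gave 16.1%, 17.9% and 20.5% for five measures two-sided, inside the range above.

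**Step 4: the ways out.** If steps alone decides, the two-sided error is 5%, and power for 1100 steps is 85.5% at 95 per arm or 87.2% at 100 per arm. If all five stay co-equal with a Bonferroni level of 0.05/5 = 0.01 each, n per group for steps becomes 2 × (2.576 + 0.842)² × 5.165 = 120.7, so 121 per group and 242 in total (246 by the t-test calculation). At that level, 95 to 100 per arm would give only 66.6% to 69.5% power.

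**The case against.** Four arguments carry weight.

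- **The any-one rule is not in the plan.** A reader might infer that the false-positive rate for Aim 3 simply is some 15-23%. The documents do not support that. The measures are joined by 'and', not by 'any of'; if all five had to be significant, the rate could not exceed that of a single test, 5%. The range also depends on assumed correlations, and values above 0.7 take it below 15%. What stands is that the success criterion is missing, so the rate is conditional.
- **Direction and content.** Hypothesis 3 is directional, so two-sided figures count results in the wrong direction and are roughly twice the rate of false claims of benefit. Self-efficacy cannot by itself show more activity, so a count of four measures is fairer for that wording. Both points stand and are reflected in the table. The favourable-direction rate is still about two to five times 2.5%.
- **Steps already looks like the lead measure.** It carries the sizing, and the Analysis Plan names it beside QOL for the comparison of treatment sequences. That suggests intent, but neither place makes it decisive for Hypothesis 3, and the hypothesis itself lists the measures unranked. This argument favours the fix.
- **Adjustment across aims.** A reader might also infer that Aims 1 to 3 need a joint correction or a fixed testing order. The plan gives a reason for treating them separately, discloses that it does not adjust, and makes no trial-level claim resting on whichever aim succeeds. A fixed order would also make an Aim 3 claim depend on the earlier aims. That is a trade-off for the sponsor, not a defect shown here.

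**Conclusion.** The concern holds within Hypothesis 3. The plan has five unranked measures, unadjusted 5% tests, no deciding measure, and a sample size built on only one of the five. As written, Aim 3 has no defined success criterion and hence no defined type I error.

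If any one significant measure were taken as support, the two-sided false-positive rate would be about 10-23% for five measures, or 9-19% for the four ActiGraph measures, across assumed common correlations from 0.9 down to 0. The rate in the intervention's favour, for five measures, would be about 5-12% against 2.5%. These figures rest on that reading of success, on the assumed correlations, and on no true effect on any of the measures. Aim 1 and Aim 2 are unaffected, and the sizing for steps is sound for a single test.

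**What to change.** State in the Analysis Plan that Hypothesis 3 is decided by one test: the change in ActiGraph steps from baseline to month 3, compared between arms by the planned two-sample t-test at two-sided 5%. State that sedentary, light and moderate minutes and self-efficacy for exercise are supportive, reported as between-arm differences with confidence intervals, and do not by themselves support a claim on Aim 3. No fixed testing order across Aims 1 to 3 is needed.

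The cost is two sentences of wording. No participants are added, all five measures are still reported, and power for steps stays at about 85% with 95 per arm. The downside is small: Aim 3 cannot be claimed on the other four measures if steps show nothing. The Randomization section keeps the arms concealed from the data-entry and analysis team until study conclusion, so the choice should be written and dated before then.
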